2.5 Determination of Sample Size

The planned sample size for this study is 32 subjects: 16 subjects of Japanese descent and 16 matched non-Hispanic Caucasian subjects.

Assuming a 25% dropout rate (based on previous clinical experience), the sample size ensures approximately 24 subjects (12 Japanese and 12 matched non-Hispanic Caucasians) complete the study, and 24 subjects are evaluable for PK analysis purposes. The sample size is considered adequate for the primary objective of the study (defined in [Section 3](#)) and therefore adequate for providing reliable estimates of PK parameters, and similarly for the secondary objective.

No formal statistical hypothesis will be tested. The sample size was based on clinical judgment, precedent PK studies of similar design, and similar subject population, not on statistical considerations such as study power. Any subject who prematurely discontinues the study, whether part of a matched pair or is not yet matched, may be replaced at the discretion of the study sponsor to ensure there are approximately 12 evaluable subjects in each ethnic group for PK analysis purposes.

3. OBJECTIVES

3.1 Primary Objective

To evaluate the PK properties of lanadelumab administered as a single SC dose of 300 mg in healthy adult volunteer subjects of Japanese descent and matched non-Hispanic, Caucasian healthy volunteer subjects.

3.2 Secondary Objective

To assess the safety and tolerability of lanadelumab administered as a single SC dose of 300 mg to healthy adult volunteer subjects of Japanese descent and matched, non-Hispanic Caucasian healthy volunteer subjects.

3.3 Exploratory Objectives

To explore the PD properties of lanadelumab including plasma kallikrein (pKal) activity and cleaved high molecular weight kininogen (cHMWK) plasma levels after a single SC dose of 300 mg of lanadelumab administered to healthy adult volunteer subjects of Japanese descent and matched non-Hispanic, Caucasian healthy volunteer subjects.

4. ANALYSIS POPULATIONS/ANALYSIS SETS

4.1 Enrolled Set

The Enrolled Set will consist of all subjects for whom an enrollment number has been assigned. Background summaries (e.g., subject disposition) will be based on the Enrolled Set, unless otherwise specified in this SAP.

4.2 Safety Analysis Set

The Safety Analysis Set will consist of all subjects who received at least 1 dose of lanadelumab (investigational product). All safety analyses will be based on the Safety Analysis Set.

4.3 Pharmacokinetic Set

The PK Set will consist of all subjects in the Safety Analysis Set who have at least 1 evaluable postdose PK concentration value. All PK analyses will be based on the PK Set.

4.4 Pharmacodynamic Set

The PD Set will consist of all subjects in the Safety Analysis Set who have at least 1 evaluable postdose PD value. All PD analyses will be based on the PD Set.

5. SUBJECT DISPOSITION

The number and percentage of subjects included in each analysis set (Enrolled, Safety, PK and PD) will be summarized as appropriate.

The number and percentage of subjects who completed the study or prematurely discontinued will be presented, along with primary reasons for discontinuation, as recorded on the study completion page of the electronic case report form (eCRF). All enrolled subjects who prematurely discontinued the study will be listed in the subject disposition listing along with reasons for discontinuation.

Subject disposition summary and listing will be based on the Enrolled Set, and the summary will be presented by ethnic group and for all groups combined.

6. PROTOCOL DEVIATIONS

Protocol deviations will be classified as major or minor in accordance with applicable Shire standard operating procedures and based on the following definitions:

- **Major protocol deviation** is a subset of protocol deviations that may significantly impact subject's rights, safety or well-being, the statistical analysis, and/or the interpretation of product safety / efficacy
- **Minor protocol deviation** is a subset of protocol deviations, which include changes or alterations in the conduct of the study that do not have a significant impact on the subject's rights, safety or well-being, or the completeness, accuracy and reliability of the study data.

All protocol deviations will be presented in the protocol deviation listing and based on the Enrolled Set. No summaries are planned.

7. DEMOGRAPHIC AND OTHER BASELINE CHARACTERISTICS

7.1 Demographic and other Baseline Characteristics

The following demographic and other baseline characteristics will be summarized by ethnic group and overall. Demographics include: age (years), sex (male, female), ethnicity (not Hispanic or Latino), and race (White, Asian). Other baseline characteristics include: weight (kg), height (cm), and BMI (kg/m^2). Note: sex, age and BMI are the matching factors.

Age will be calculated as the integer part of: $(\text{date of screening} - \text{date of birth} + 1)/365.25$, and BMI will be calculated as: $\text{weight (kg)} / (\text{height [m]})^2$. Height and weight at screening assessment will be used to calculate BMI.

Continuous variables, such as age, weight, height, and BMI will be summarized using descriptive statistics including n, mean, SD, median, minimum, and maximum. Categorical variables such as sex, ethnicity, and race will be summarized by reporting the number and percentage of subjects in each category.

All demographic and other baseline characteristics variables that will be summarized will be taken from the Screening Visit. Summaries will be based on the Safety Analysis Set, PK Set and PD Set, as appropriate. Demographics and other baseline characteristics data will be listed, and the listing will be based on the Safety Analysis Set. Subject matching will be listed only, and the listing will be based on the Enrolled Set.

7.2 Medical History

A complete medical and medication history will be collected at the Screening Visit including recent use of medication (30 days prior to entering the screening period) and history of respiratory, cardiovascular, renal, gastrointestinal, hepatic, endocrine, hematological, neurological, psychiatric, and other diseases.

Medical history will be coded using the Medical Dictionary for Regulatory Activities (MedDRA, version 20.1 or higher).

Medical history will be listed and summarized by system organ class (SOC) and preferred term (PT), and based on the Safety Analysis Set. The summary will include number and percentage of subjects who experienced the event, and number of events experienced. SOC will be sorted alphabetically, and PT will be sorted within each SOC in descending frequency in the table Total column (i.e., the Total column will be sorted in descending order after sorting by SOC and PT).

8. EXTENT OF EXPOSURE AND TREATMENT COMPLIANCE

8.1 Exposure to Investigational product

Exposure in this single-dose (300 mg, single-administration) study will be summarized in terms of the total dose (mg) administered and summarized by ethnic group and overall.

Total dose administered (mg) will be calculated as follows:

$$\text{Total dose administered (mg)} = \text{Planned dose (mg)} \times \frac{\text{Total volume administered (mL)}}{\text{Planned volume (mL)}}$$

where the planned dose is 300 mg; the planned volume is 2 mL; and the total volume administered will be collected in the eCRF.

Summary will include: n, mean, SD, median, minimum, and maximum, and based on the Safety Analysis Set. An exposure data listing, based on the Safety Analysis Set, will be provided and include date and time of dose administration and other exposure data, e.g. planned dose/volume, total dose/volume and location of dose.

8.2 Measurement of Treatment Compliance

This is a single-dose (single-administration) study in which the investigational product will be administered on Day 1 to all subjects and at the study site only (in-house confinement treatment period). All compliance-related data will be included in the exposure data listing. No separate treatment compliance summary or data listing will be provided.

9. PRIOR AND CONCOMITANT MEDICATIONS

Prior and concomitant medications will be coded using the World Health Organization-Drug Dictionary (WHO-DD) Version September 2017 or higher.

For statistical analysis purposes, prior and concomitant medications are defined as follow (“time” implies date and time):

- **Prior medication:** Any medication with start time **prior to** time of investigational product administration.
- **Concomitant medication:** Any medication with start time **at or after** time of investigational product administration, OR medications with start time **prior to** investigational product administration but continuing at or after investigational product administration. Any medication with a start date after the end of the follow-up period (Day 112/ End of Study Visit) will be considered post-treatment medication and not concomitant medication.

For medications with partial onset times, non-missing date parts will be used to determine if the medication is concomitant or prior medication. If a determination cannot be made using the non-missing date parts as to when the medication occurred relative to investigational product administration then the medication will be classified as concomitant medication. Additional information is provided in [Section 18.5](#).

Both prior and concomitant medication usage will be summarized by therapeutic class and preferred term, and based on the Safety Analysis Set. The summary will include number and percentage of subjects who took the medication. Therapeutic class will be sorted alphabetically, and PT will be sorted within each therapeutic class in descending frequency in the table Total column (i.e., the Total column will be sorted in descending order after sorting by therapeutic class and PT). Medications can be counted both as prior and concomitant medications. Multiple medication usage by a subject in the same PT will be counted only once for that PT. All prior and concomitant medications will be listed, and the listings will be based on the Safety Analysis Set.

10. EFFICACY ANALYSES

Not applicable.

11. SAFETY ANALYSES

Safety endpoints include the occurrence and number of treatment-emergent adverse events (TEAEs), vital signs (systolic and diastolic blood pressure, pulse rate, and body temperature), electrocardiogram (ECG) results, body weight, clinical laboratory test results (hematology, clinical chemistry, coagulation and urinalysis), and immunogenicity response (development of anti-drug antibodies [ADAs]). For each safety endpoint, unless otherwise specified, the last non-missing value before the administration of investigational product will be used as **baseline** for all analyses of that safety endpoint.

All safety analyses will be descriptive and based on the Safety Analysis Set. Continuous variable summaries will include: number of subjects (n), mean, SD, median, minimum and maximum values, and categorical variable summaries will include: number and percentage of subjects.

11.1 Adverse Events

Adverse events (AEs) will be coded using the MedDRA (Version 20.1 or higher).

Treatment-emergent AEs are AEs with onset at the time of or following the first exposure to investigational product, or medical conditions present prior to the start of investigational product but increased in severity or relationship at the time of or following the start of treatment, up to the last follow-up visit. **Note:** In this study, all AEs will be collected from the time the informed consent is signed through the last follow-up visit (Day 112/End of Study).

An overall summary of the number of subjects with TEAEs will be presented, including, but not limited to: the number and percentage of subjects with any TEAEs, severe TEAEs, serious TEAEs, TEAEs related to investigational product, TEAEs leading to discontinuation from the study, TEAEs resulting in hospitalization, and TEAEs leading to death. An overall summary of the number of TEAEs will be summarized also.

In addition, the number of TEAEs and number and percentage of subjects reporting TEAEs will be tabulated by SOC and PT. The number and percentage of subjects reporting TEAEs will be summarized by SOC, PT, and maximum severity, as appropriate, based on applicable Shire TFL standards. (Note: all severity levels will be presented in the summary). SOC will be sorted alphabetically, and PT will be sorted within each SOC in descending frequency in the table Total column (i.e., the Total column will be sorted in descending order after the sorting by SOC and PT). Also, all TEAEs and related TEAEs will each be summarized by PT only and in decreasing frequency in the table Total column, and separately non-SAEs will be summarized by SOC and PT and sorted as planned for the other summaries. TEAEs considered related to investigational product will also be summarized by SOC and PT. If more than 1 TEAE occurs within the same PT for the same subject, then the subject will be counted only once for that PT using the most severe and most related occurrence for the summarization by severity and by relationship to investigational product. For example, if a subject experienced a mild headache not related to investigational product, and a moderate headache related to investigational product, then the subject will be counted once for headache using the moderate headache related to investigational product.

Serious TEAEs, TEAEs related to investigational product, TEAEs leading to discontinuation from the study, and TEAEs leading to death will be summarized by SOC and PT. Injection site reactions (ISRs) are not predefined in the study protocol. Any ISRs, if reported as AEs, will be summarized along with all other TEAEs as appropriate.

All AE data will be listed. Listings will be presented for all AEs (TEAEs and non-TEAEs), serious AEs, severity of AEs, AEs related to investigational product, AEs leading to discontinuation from the study, and AEs leading to death.

All TEAE summaries will be based on the Safety Analysis Set. Listings will be based on all enrolled subjects.

11.2 Clinical Laboratory Variables

Raw (actual) clinical laboratory values (in SI units) and changes in raw values from baseline at each post-baseline assessment time point will be summarized as continuous variables. Shift tables from baseline to each assessment time point will be provided for categorical variables. The following laboratory variables/parameters will be summarized:

Hematology	Hemoglobin, hematocrit, red blood cells (RBC), platelet count, white blood cell (WBC) count – total and differential, total neutrophils (absolute), eosinophils (absolute), monocytes (absolute), basophils (absolute), and lymphocytes (absolute).
Coagulation	Prothrombin Time, activated partial thromboplastin time, and international normalized ratio
Biochemistry	Sodium, potassium, glucose, blood urea nitrogen (BUN), creatinine, calcium, chloride, phosphorus, total protein, total CO ₂ (bicarbonate), albumin, aspartate transaminase (AST), alanine transaminase (ALT), gamma glutamyl transferase (GGT), alkaline phosphatase (ALP), total bilirubin, and uric acid.
Urinalysis	pH, glucose, protein, blood, ketones, bilirubin, nitrites, leukocyte esterase, and specific gravity.

Clinical laboratory test values are potentially clinically important (PCI) if they meet either the low or high PCI criteria listed in [Table 3](#) and [Table 4](#). The number and percentage of subjects with post-baseline PCI values at each scheduled time point will be tabulated for each set of PCI criteria. The percentages will be calculated relative to the number of subjects with available baseline values and at least 1 post-baseline assessment. The numerator is the total number of subjects with at least 1 post-baseline PCI value. A supportive listing of subjects with post-baseline PCI values will be provided for each set of PCI criteria including the subject number, baseline, and post-baseline values.

All clinical laboratory data will be listed, and listings will be based on the Safety Analysis Set.

Table 3: Primary Criteria for Potentially Clinically Important Laboratory Tests

Parameter	Classification	Criteria
Biochemistry		
Sodium	HIGH	> 5 mmol/L (5 mEq/L) above ULN
	LOW	> 5 mmol/L (5 mEq/L) below LLN
Potassium	HIGH + INCREASE	Above ULN and increase of > 0.5 mmol/L (0.5 mEq/L) from baseline value
	LOW + DECREASE	Below LLN and decrease of > 0.5 mmol/L (0.5 mEq/L) from baseline value
Creatinine	HIGH + INCREASE	> 150µmol/L and increase > 30% from baseline value
BUN	HIGH	> 1.5 x ULN
Glucose (fasting)	HIGH	≥ 6.7 mmol/L
	LOW	≤ 4.2 mmol/L
Calcium	HIGH and INCREASE	Above ULN and Increase of ≥ 0.25 mmol/L (1.0 mg/dL) from baseline value
	LOW and DECREASE	Below LLN and Decrease of ≥ 0.25 mmol/L (1.0 mg/dL) from baseline value
Phosphorus	HIGH	> 0.162 mmol/L (0.5 mg/dL) above ULN
	LOW	> 0.162 mmol/L (0.5 mg/dL) below LLN
Total protein	HIGH and INCREASE	Above ULN and Increase of ≥ 20 g/L (2.0 g/dL) from baseline value
	LOW and DECREASE	Below LLN and Decrease of ≥ 20 g/L (2.0 g/dL) from baseline value
Albumin	HIGH and INCREASE	Above ULN and Increase of ≥ 10 g/L (1.0 g/dL) from baseline value
	LOW and DECREASE	Below LLN and Decrease of ≥ 10 g/L (1.0 g/dL) from baseline value
Uric acid (with normal diet)	HIGH and INCREASE	Above ULN and Increase of > 0.119 mmol/L (2.0 mg/dL) from baseline value
	LOW and DECREASE	Below LLN and Decrease of > 0.119 mmol/L (2.0 mg/dL) from baseline value
ALT	HIGH	> 2 x ULN
AST	HIGH	> 2 x ULN
ALP	HIGH	> 1.5 x ULN
GGT	HIGH	> 1.5 x ULN
Total bilirubin	HIGH	> 1.5 x ULN
T4	HIGH	> 140.28 nmol/L
	LOW	< 57.92 nmol/L
T3	HIGH	> 2.765 nmol/L
	LOW	< 0.922 nmol/L
TSH	HIGH	>5.0 µU/mL
	LOW	<0.5 µU/mL

Parameter	Classification	Criteria
Hematology		
RBC count	HIGH	>7.5 x10 ¹² /L
	LOW	<3 x10 ¹² /L
Hematocrit	HIGH	>1.3 x ULN
	LOW and DECREASE	≤0.6 x LLN and Decrease of ≥ 0.06 L/L (6.0%) from baseline value
Hemoglobin	HIGH	>200 g/L (20g/dL)
	LOW and DECREASE	< 100g/L (10g/dL) and Decrease of ≥ 20g/L (2.0 g/dL) from baseline value
WBC count	HIGH	>2 x ULN OR >16.0 x 10 ⁹ /L (16 x 10 ³ /μL)
	LOW	< 0.5 x LLN OR < 3.0 x 10 ⁹ /L (3 x 10 ³ /μL)
Neutrophils	HIGH	> 6.2 x 10 ⁹ /L (6.2 x 10 ³ /μL) OR > 70 %
	LOW	< 1.5 x 10 ⁹ /L (1.5 x 10 ³ /μL) OR < 40%
Lymphocytes	HIGH	> 4.0 x 10 ⁹ /L (1.5 x 10 ³ /μL) OR > 44 %
	LOW	< 0.8 x 10 ⁹ /L (0.8 x 10 ³ /μL) OR < 22 %
Monocytes	HIGH	> 1.1 x 10 ⁹ /L (1.1 x 10 ³ /μL) or > 11%
Eosinophils	HIGH	> 0.5 x 10 ⁹ /L (> 500/μL) and > 10.0%
	LOW	NA
Basophils	HIGH	> 0.2 x 10 ⁹ /L (0.2 x 10 ³ /μL) or > 2%
	LOW	NA
Platelet count (thrombocytes)	HIGH	>1.5 x ULN OR > 500 x 10 ⁹ /L (100 x 10 ³ /μL)
	LOW	<0.6 x LLN OR < 100 x 10 ⁹ /L (100 x 10 ³ /μL)
Urinalysis		
Glucose	HIGH	≥ 1+
Blood	HIGH	≥ 2+
Bilirubin		Positive
Protein	HIGH	≥ 2+
Nitrite		Positive
Ketones	HIGH	≥ 2+
Leukocyte Esterase		Positive
BUN: blood urea nitrogen, AST: aspartate transaminase, ALT: alanine transaminase, ALP: alkaline phosphatase, GGT: gamma glutamyl transferase, T3: triiodothyronine, T4: thyroxine, TSH: thyroid-stimulating hormone, RBC: red blood cell, WBC: white blood cell, NA: not available.		

Table 4: Secondary Criteria for Potentially Clinically Important Laboratory Tests

Parameter	Classification	Criteria
Biochemistry		
Sodium	HIGH	≥ 148 mEq/L
	LOW	≤ 129 mEq/L
Potassium	HIGH	≥ 5.5 mEq/L
	LOW	≤ 3.2 mEq/L
Creatinine	HIGH	≥ 2.1 mg/dL
BUN	HIGH	> 31 mg/dL
Glucose (fasting)	HIGH	> 125 mg/dL
	LOW	≤ 54 mg/dL
Calcium	HIGH	≥ 11.6 mg/dL
	LOW	≤ 7.4 mg/dL
Phosphorus	HIGH	NA
	LOW	≤ 1.9 mg/dL
Total protein	HIGH	NA
	LOW	< 5.0 g/dL
Albumin	HIGH	NA
	LOW	< 2.5 g/dL
ALT	HIGH	≥ 5.1 x ULN
AST	HIGH	≥ 5.1 x ULN
ALP	HIGH	≥ 3.1 x ULN
Total bilirubin	HIGH	≥ 1.51 x ULN
Hematology		
Hemoglobin (Female)	HIGH	NA
	LOW and DECREASE	≤ 9.4 gm/dL and Decrease of ≥ 2.1 gm/dL from baseline value
Hemoglobin (Male)	HIGH	NA
	LOW and DECREASE	≤ 10.4 gm/dL and Decrease of ≥ 2.1 gm/dL from baseline value
WBC count	INCREASE	$\geq 20,001$ cell/mm ³
	DECREASE	$\leq 1,499$ cell/mm ³
Neutrophils	HIGH	NA
	DECREASE	≤ 999 cell/mm ³
Lymphocytes	HIGH	NA
	DECREASE	≤ 499 cell/mm ³
Eosinophils	HIGH	> 5000 cell/mm ³
	LOW	NA

Parameter	Classification	Criteria
Platelet count (thrombocytes)	HIGH	NA
	LOW	$\leq 99,000 \text{ cell/mm}^3$
Urinalysis		
Glucose	HIGH	$\geq 2+$
Protein	HIGH	$\geq 2+$
BUN: blood urea nitrogen, AST: aspartate transaminase, ALT: alanine transaminase, ALP: alkaline phosphatase, WBC: white blood cell, NA: not available. Based on Grade 3 or Grade 4 criteria from Toxicity Grading Scale for Healthy Adult and Adolescent Volunteers Enrolled in Preventive Vaccine Clinical Trials (FDA Guidance for Industry, September 2007) .		

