11.3 Vital Signs (Including Height and Weight)

Raw (actual) values for vital signs (e.g., systolic and diastolic blood pressure, pulse rate, and body temperature) and their changes from baseline at each post-baseline assessment time point will be summarized.

Vital sign values will be considered PCI if they meet both the observed value criteria and the change from baseline criteria listed in [Table 5](#). The number and percentage of subjects with PCI post-baseline values at each scheduled time point will be tabulated. The percentages will be calculated relative to the number of subjects with baseline and at least 1 post-baseline assessment. The numerator is the total number of subjects with at least 1 PCI post-baseline vital sign value. A supportive listing of subjects with post-baseline PCI values will be provided including the subject number, baseline, and post-baseline PCI values.

All vital signs data (including height and weight) will be listed, and listing(s) will be based on the Safety Analysis Set.

Table 5: Criteria for Potentially Clinically Significant Vital Signs

Parameter	Classification	Criteria
Systolic blood pressure (mm Hg)	HIGH and INCREASE	≥ 140 and increase of ≥ 20 from baseline value
	LOW and DECREASE	≤ 90 and decrease of ≥ 20 from baseline value
Diastolic blood pressure (mm Hg)	HIGH and INCREASE	≥ 90 and increase of ≥ 15 from baseline value
	LOW and DECREASE	≤ 50 and decrease of ≥ 15 from baseline value
Pulse rate (bpm)	HIGH and INCREASE	≥ 100 and increase of > 15 from baseline value
	LOW and DECREASE	≤ 45 and decrease of > 15 from baseline value
Temperature	HIGH	$> 38.3^\circ\text{C}$ or $> 100.9^\circ\text{F}$
	LOW	$< 35^\circ\text{C}$ or $< 95^\circ\text{F}$

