11.4 Electrocardiogram (ECG)

Raw (actual) values for ECG variables (e.g., heart rate, RR interval, PR interval, QRS interval, QT interval, and QTc interval) and their changes from baseline at each post-baseline assessment time point will be presented. QTc interval will be calculated using both Bazett ($QTcB=QT/(RR)^{1/2}$) and Fridericia ($QTcF=QT/(RR)^{1/3}$) corrections; and if RR is not available, then 60/heart rate will be used in the correction formula. Electrocardiogram interpretation, per the investigator, will be summarized by assessment time point for all scheduled assessments. In addition, a shift table from baseline to each post-baseline assessment time point for categorical ECG results will be provided.

Subject's baseline ECG is defined as the single ECG collected predose on Day 1 (or unscheduled ECG collected after the scheduled predose timepoint but prior to the administration of investigational product).

Electrocardiogram variable values will be considered PCI if they meet or exceed the upper limit values listed in [Table 6](#). The number and percentage of subjects with post-baseline PCI values at each scheduled time point will be tabulated. The percentages will be calculated relative to the number of subjects with available non-PCI baseline and at least 1 post-baseline assessment. The numerator is the total number of subjects with at least 1 PCI post-baseline ECG value. A listing of all subjects with post-baseline PCI values will be provided including the subject number, baseline, and post-baseline PCI values.

All ECG data will be listed, and listing will be based on the Safety Analysis Set. Listings of ECG data, including interpretation by individual subject, will also be produced.

Table 6: Criteria for Potentially Clinically Important ECG Values

Parameter	Classification	Criteria
Overall Evaluation	ABNORMAL	Overall Evaluation is ABNORMAL
Heart rate (bpm)	HIGH and INCREASE	≥ 100 and increase of > 15 from baseline value
	LOW and DECREASE	≤ 45 and decrease of > 15 from baseline value
PR interval (msec)	HIGH and INCREASE	≥ 200 and increase of ≥ 20 from baseline value
QRS interval (msec)	HIGH	≥ 120
QTc interval (men) (msec)	HIGH	> 430 and increase from baseline value > 30
QTc interval (women) (msec)	HIGH	> 450 and increase from baseline value > 30

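### For criteria that are a limit only, the laboratory and temperature PCI percentages mix abnormalities present before dosing with new ones

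*SAP*

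**What the plan says.** SAP 11.2 defines the laboratory PCI percentage in two sentences. For the denominator: "The percentages will be calculated relative to the number of subjects with available baseline values and at least 1 post-baseline assessment". For the numerator: "The numerator is the total number of subjects with at least 1 post-baseline PCI value". Neither sentence asks whether the baseline value was itself PCI. Baseline is defined in SAP 11: "the last non-missing value before the administration of investigational product will be used as" baseline.

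The other safety domains use different rules.

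- **ECG (SAP 11.4):** "The percentages will be calculated relative to the number of subjects with available non-PCI baseline and at least 1 post-baseline assessment". The numerator sentence there carries no baseline condition.
- **Vital signs (SAP 11.3):** the denominator is built as for laboratory values, but "Vital sign values will be considered PCI if they meet both the observed value criteria and the change from baseline criteria". In Table 5 the two temperature rows give a limit and no change, so this safeguard does not reach temperature.

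Within the laboratory tables, some criteria include a change. High potassium, for example, is defined as: "Above ULN and increase of > 0.5 mmol/L (0.5 mEq/L) from baseline value". Most are a limit alone.

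SAP 11.2 also plans summaries of change from baseline. It adds: "Shift tables from baseline to each assessment time point will be provided for categorical variables". A PCI listing is planned "including the subject number, baseline, and post-baseline values".

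**The concern.** Every subject receives lanadelumab and there is no placebo group, so each subject's own baseline is the only reference for a drug effect. If a subject's lymphocyte percentage is above 44% on Day -1 and stays there, the planned table reports a post-baseline PCI finding for that subject even though nothing has changed.

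The PCI tables are presented by ethnic group, and safety and tolerability are the secondary objective. Matching covers sex, age and BMI, not laboratory values. Eligibility removes only laboratory abnormalities that the investigator judges clinically significant (Protocol 4.2, criterion 16), so subjects beyond the looser PCI limits can be dosed. With groups this small, one or two such subjects visibly move a percentage, and a chance imbalance at baseline could be read as a difference in tolerability. The study is meant to support extrapolation to Japanese patients, so such a difference would have to be explained.

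**Working it through.** The documents give no PCI percentage to reproduce. The check counts the criteria affected, then sizes the effect.

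**1. Criteria count.** Each high, low or positive row is classed by whether its criterion text includes a change from baseline. In Table 4 some white-cell rows are labelled as an increase or decrease but state only a limit; they are classed as limit-only. The six thyroid rows of Table 3 are left out because those tests are drawn at Screening only.

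| Table | Limit only | Change required | Total |
|---|---|---|---|
| 3, biochemistry | 12 | 11 | 23 |
| 3, hematology | 15 | 2 | 17 |
| 3, urinalysis | 7 | 0 | 7 |
| **3, all** | **34 (72%)** | **13 (28%)** | **47** |
| **4, all** | **25 (93%)** | **2 (7%)** | **27** |

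The change-required criteria are potassium, creatinine, calcium, total protein, albumin, uric acid, low hematocrit and low hemoglobin in Table 3, and low hemoglobin (female and male rows) in Table 4. A baseline value cannot meet these.

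**2. Weight of one subject.** SAP 2.5 plans 16 per group and assumes 25% dropout: 32 × 0.75 = 24, or 12 per group. One subject who is PCI at baseline and stays so adds 1/16 = 6.25 points, or 1/12 = 8.3 points.

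**3. Worked example (assumed counts, 16 per group).** Three Japanese and no Caucasian subjects are PCI at baseline and remain so.

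| New cases per group | Planned rule | Non-PCI baseline only |
|---|---|---|
| 0 | 3/16 = 18.8% vs 0/16 = 0% | 0/13 = 0% vs 0/16 = 0% |
| 1 | 4/16 = 25.0% vs 1/16 = 6.25% | 1/13 = 7.7% vs 1/16 = 6.25% |

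**4. Expected spurious difference.** Let b be the share PCI at baseline, π the chance that such a subject is PCI after dosing, and q the new-onset rate, with π and q equal in both groups. A group's planned rate is bπ + (1 − b)q, so the expected difference is (b_J − b_C)(π − q). None of these inputs is in the documents. For baseline gaps of 5 to 20 points, π of 0.5 to 1 and q of 0 to 0.10, it runs from 0.05 × (0.5 − 0.10) = 2.0 points to 0.20 × (1 − 0) = 20.0 points.

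**5. Share of counted subjects already PCI at baseline.** A simulation used a normal model with one baseline and 10 post-dose draws (Day 2, Day 5 and eight out-patient visits). The exceedance probability and the within-subject correlation r are assumptions.

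| Exceedance | r | Single visit | Any of 10 draws |
|---|---|---|---|
| 5% | 0.5 | about 24% | about 15% |
| 5% | 0.7 | about 39% | about 23% |
| 5% | 0.85 | about 56% | about 34% |
| 1% | 0.7 | about 27% | about 15% |

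**6. What restriction to a non-PCI baseline achieves.** Same model, with no drug effect and assumed exceedance of 5% in one group and 15% in the other.

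| r | Reading | Planned difference | Restricted difference |
|---|---|---|---|
| 0.7 | Single visit | 10 points | about 5 points |
| 0.7 | Any of 10 draws | about 23 points (18.5% vs 41.4%) | about 17 points (15.0% vs 32.3%) |
| 0.85 | Single visit | 10 points | about 4 points |
| 0.85 | Any of 10 draws | about 19 points | about 12 points |

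One baseline draw does not identify every subject who lives near the limit, so part of the difference remains.

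**The case against.** **The SAP does not call these values treatment-emergent.** It promises post-baseline PCI values, and counting every value beyond a limit is a legitimate description. The baseline-referenced view comes from the change summaries, the shift tables, the listing with baseline values and the adverse event tables; with 16 per group, cases can be read one by one. This stands in part. A careful reader can find the problem, but the percentage remains uncorrected and the SAP does not define its shift categories by PCI status.

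**Counting criteria overstates exposure.** Many of the 34 limits are extreme for healthy volunteers, such as red cell count above 7.5 or below 3 × 10¹²/L, or ALT above twice the upper limit. Baseline positivity is plausible mainly for loose limits: neutrophil or lymphocyte percentages, or fasting glucose at or below 4.2 mmol/L. This stands: 72% is a share of criteria, not of expected findings.

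**The ECG rule is an incomplete precedent.** It restricts the denominator but not the numerator sentence. This stands, and a fix should restrict both.

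**Dropping baseline-PCI subjects hides worsening.** Table 4 would not always recover them; for platelets its low limit (at or below 99,000 cells/mm³) nearly equals the absolute low limit in Table 3 (below 100 × 10⁹/L). This stands against simple exclusion, but not against a separate row.

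**Conclusion.** The point holds for limit-only criteria: 34 of 47 in Table 3, 25 of 27 in Table 4, and temperature in Table 5. There the planned percentage combines pre-existing with new findings. The certain part is arithmetic: each persisting baseline-PCI subject adds 6.25 points in a group of 16. The 2 to 20 point range and the simulated shares rest on assumed baseline rates, persistence and correlation.

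A reader might infer more than the documents support:

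- That any baseline laboratory difference between the groups becomes a safety difference. Only a difference in the share of subjects beyond a PCI limit that persists after dosing can do so. A subject who returns within the limit at every post-dose draw is not counted.
- That all laboratory PCI percentages are affected. The 13 change-required criteria in Table 3 and the two in Table 4 are not.
- That the two groups do differ at baseline. Nothing in the documents shows this; the 5% against 15% case is an illustration.
- That restricting to a non-PCI baseline removes a false difference. Under the assumed model, much of it remains.

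No hypothesis is tested, so the effect is on the descriptive reading of the secondary objective. The correction is worth making because it is cheap and uses data already planned.

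**What to change.** In SAP 11.2, for the limit-only criteria of Tables 3 and 4, and in SAP 11.3 for temperature, tabulate PCI by baseline PCI status for the same criterion:

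- **New onset:** numerator and denominator both limited to subjects with a baseline value that is not PCI for that criterion and at least one post-baseline assessment.
- **PCI at baseline:** a separate row giving the number of such subjects and how many are PCI after dosing, with the listing kept as planned so that worsening stays visible.

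Criteria that require a change stay as they are. A footnote should say that a single baseline draw does not identify every subject near a limit, so a remaining group difference is not by itself evidence of a drug effect.

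The cost is a short SAP wording change, one programming condition, extra table rows, and slightly smaller denominators where some subjects are PCI at baseline. No additional data are needed.
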